The design corresponds to a single-center, open, non-inferiority, controlled, randomized clinical trial. The trial will be blind for the patient and to the investigator that will evaluate the morbidities in the postoperative time, only the surgeon knows which technique is used.

The target population will be those over 18 and under 70 years of age, undergoing coordination coronary revascularization surgery, in which it is necessary to use the internal saphenous vein as a conduit. Those who do not meet the entry criteria, emergency surgeries, patients with poor metabolic control ($\text{HbA1c} > 6.5\%$), chronic venous insufficiency or chronic obstructive arteriopathy of the lower limbs, and type II obesity ($\text{BMI} > 35$) will be excluded.

Given that the number of patients assigned to each group is required to be similar throughout the study, the randomization method that we believe is most appropriate is assignment through permuted block randomization of four.

Evaluations will be carried out in person before discharge from the hospital, approximately one week after the operation. Subsequently, in-person assessments will be conducted at the one-month follow-up, and finally, telephone assessments will be conducted at six months. The assessment will be carried out by researchers who are blind to the randomization group and will record on a form, indicating the presence (1) or absence (0) of the following aspects: local infection requiring antibiotics, hematoma, blisters, secretions, necrosis and dehiscence of the wound. . As for the rest of the variables, such as paresthesias, pain and functional impotence, they will be recorded according to the pain scale from 0 to 10.

The data of each patient will be grouped into tables, including relevant personal history and answers to the questionnaires. The analysis will then be carried out from these forms using the corresponding analytical tests.

A monitoring and safety committee will be appointed that will continuously evaluate adverse effects (included in the primary objective) as well as clinical results (operative and 1-year mortality) and will consider suspension of the study in the event of a significant increase.

Sample calculation:

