A probability of complication of saphenectomy by conventional or "control" technique of 10% was assumed, based on studies from our institution, and according to preliminary studies we expect to find 50% more in the "no touch" technique, therefore 15%. To determine the non-inferiority margin, 10 patients who were recently revascularized, 5 men and 5 women, were asked how many times more pain or local infection they were willing to accept with the "no touch" technique in exchange for greater bypass patency. short and long term. When analyzing the results, it is obtained that they would be willing to accept up to twice as many complications by applying the "no touch" technique, therefore the non-inferiority limit will be 20%. With these values, assuming a 95% confidence interval and a power (1 - beta) of 80%, and taking into account a probable 20% of lost patients, we can calculate the necessary population sample size, which was in total 52 patients; 26 people in the group with conventional technique and 26 in the "no touch".

Informed consent:

Two informed consents have been prepared that cover details about the research, its duration and relevance, the procedure to be performed, as well as the associated risks and benefits. In preoperative evaluations, the surgical team personnel will be responsible for obtaining this consent. In this document, the patient will have the opportunity to express their willingness to participate or not in the research.

Institution:

The study will be carried out at the Instituto Nacional de Cirugía Cardíaca, a medical care institution dedicated to the diagnosis and treatment of cardiovascular conditions, the first institute of cardiac surgery and hemodynamics in the country with more than 50 years of experience. Located at the address [name], SMI Hospital, [contact], email [contact].

Schedule:

The schedule consists of a first stage where the surgeries of the 52 patients will be performed, we estimate 9 months. The second stage will be data collection, 3 controls will be carried out: 7 days after surgery, in the polyclinic approximately one month later, and 6 months later by phone call.

After one year, a coronary CT angiography will be performed to evaluate the patency of the bypasses. The data will be grouped into tables by the team of researchers. The duration of the first stage will be from the first surgery to the last, we estimate that it will be 6 months.

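### The 95% interval has no stated sidedness, and 52 patients fall well short of the claimed 80% power at either level when the expected difference is taken in the plan's own direction

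*Combined protocol and SAP*

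**What the plan says.** The Sample calculation section contains the plan's only statement of error level: "assuming a 95% confidence interval and a power (1 - beta) of 80" per cent. Its other inputs are:

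- Conventional arm: "A probability of complication of saphenectomy by conventional or 'control' technique of 10% was assumed".
- No-touch arm: "we expect to find 50% more in the 'no touch' technique, therefore 15" per cent.
- Margin: "therefore the non-inferiority limit will be 20" per cent, derived from patients' willingness to accept up to twice as many complications.
- Loss: 20%.

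The result is a sample "which was in total 52 patients; 26 people in the group with conventional technique and 26 in the 'no touch" arm. The tool is cited in Bibliography item 16, an online calculator for binary non-inferiority, without the values entered.

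For the analysis, Methodology says only: "The analysis will then be carried out from these forms using the corresponding analytical tests". The hypotheses under Objectives name no level. No section gives an alpha, says whether the 95% interval is one- or two-sided, or states the rule by which non-inferiority will be concluded.

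**The concern.** A two-sided 95% interval used for non-inferiority is a one-sided 2.5% test. A one-sided 95% bound is a one-sided 5% test, equivalent to a two-sided 90% interval. The plan's words fit either, and the error rate differs by a factor of two. With few events per arm, a borderline result can pass at one level and fail at the other. Since no rule is fixed, the choice could be made after the data are seen.

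The sample size ought to show which level was meant. Trying to recover it raises a second problem: the 80% power claim does not follow from the plan's inputs, at either level, when no-touch is assumed to have more complications, as the plan says.

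**Working it through.** **Inputs** (Sample calculation): conventional 10%, no-touch 15%, limit 20% (read first as 20 points), power 80%, loss 20%, equal allocation.

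**Formula** (normal, unpooled), per arm:

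n = (z_alpha + z_0.80)^2 x [0.10 x 0.90 + 0.15 x 0.85] / D^2

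Here D is the distance from the expected difference to the margin. The variance term is 0.0900 + 0.1275 = 0.2175. The squared sum is (1.645 + 0.842)^2 = 6.183 at one-sided 5% and (1.960 + 0.842)^2 = 7.849 at one-sided 2.5%.

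**1. Reproducing 52.** Take D = 0.20 + 0.05 = 0.25, which treats the 5-point excess as an advantage of no-touch.

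- One-sided 5%: 6.183 x 0.2175 / 0.0625 = 21.52. Then 21.52 x 1.2 = 25.8, so 26 per arm and 52 in total. This matches. Dividing by 0.8 instead gives 26.9, so 27 per arm, which does not.
- One-sided 2.5%: 7.849 x 0.2175 / 0.0625 = 27.31, so 28 per arm before loss. With loss, 27.31 x 1.2 = 32.8, so 33, and 28 / 0.8 = 35.

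**2. Other readings**, per arm before loss:

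| Reading | One-sided 5% | One-sided 2.5% |
|---|---|---|
| Stated direction, 20-point limit (D = 0.15) | 59.8 | 75.9 |
| Equal 10% rates, 20-point limit | 27.8 | 35.3 |
| Equal 15% rates, 20-point limit | 39.4 | 50.0 |
| Stated direction, 10-point limit (D = 0.05) | 538 | 683 |

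None gives 26 per arm, with or without loss. In the stated direction with a 20-point limit, the total with loss is 144 to 150 at one-sided 5% and 184 to 190 at one-sided 2.5%.

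**3. Power of 52 patients in the stated direction.** Power = Phi(D/SE - z_alpha), with SE = sqrt(0.2175/n).

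- n = 26: SE = 0.0915 and 0.15/0.0915 = 1.640. Power is Phi(1.640 - 1.645) = 50% or Phi(1.640 - 1.960) = 37%.
- n = 21 (26 x 0.8 = 20.8): SE = 0.1018 and 0.15/0.1018 = 1.474. Power is 43% or 31%.
- Full enumeration of both binomials with the Farrington-Manning score test gives 45% or 33% with 26 per arm, and 39% or 26% with 21.
- If the limit is a 20% ceiling (10 points above the 10% control rate), D = 0.05 and the formula gives 14% or 8% with 26 per arm, and 12% or 7% with 21.

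**4. How often the level decides the verdict**, at true rates of 10% and 15%:

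- 20-point limit, 26 per arm: 13% of trials with the score test, 10% with the Wald interval. With 21 per arm: 13% with either.
- 10-point limit: about 6%.
- False-positive rate at the 20-point limit (10% v 30%, 26 per arm, score test): 4.9% at one-sided 5%, 2.5% at one-sided 2.5%.

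One example that changes under both tests is 5 events in each arm of 26. The Wald standard error is sqrt(2 x (5/26) x (21/26) / 26) = 0.109, so the upper limit is 1.645 x 0.109 = 18.0 points with a 90% interval and 1.960 x 0.109 = 21.4 points with a 95% interval. The score statistic is 1.78, between 1.645 and 1.960.

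**The case against.** **A reader might infer that the plan contradicts itself, stating 95% but computing at 90%.** The documents do not support that. They never call the interval two-sided, non-inferiority is a one-sided question, and a one-sided 95% bound is a one-sided 5% test. What is established is a missing sidedness.

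**A reader might also infer that 52 is adequate at one-sided 5%.** It is not. The match also needs the excess of complications counted in favour of no-touch, and loss applied as a multiplier. The direction matters far more than the level: it moves the size by a factor of 59.8/21.5 = 2.8, and alpha by 27.3/21.5 = 1.27.

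**The route to 52 is inferred.** Once input errors are allowed, others can be built. At one-sided 2.5%, a 20-point distance with the 10%/15% variance gives 42.7 x 1.2 = 51.2, hence 52 if a per-arm figure were taken for the total. Nothing shows that this happened, but back-solving alpha from the sample size is not proof. Also, 26 evaluable per arm at one-sided 2.5% with D = 0.25 has 78% power, close to 80%, though only by ignoring the loss that the plan says it included. This objection stands.

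**The discordance figures depend on the test and the margin.** That stands too. With 26 per arm, results of 2 v 3, 1 v 2 and 4 v 4 events (conventional v no-touch) change verdict under the score test but pass at both levels under the Wald interval. With a 10-point limit, these three and 5 v 5 all fail at both levels.

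**Conclusion.** The concern holds as an unstated level combined with an unsupported power claim. The plan fixes no alpha, sidedness or decision rule, so a borderline verdict would depend on a choice not yet made, in about 10 to 13% of trials under a 20-point limit and about 6% under a 10-point limit.

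The claimed 80% power is not met under either reading of 95%. In the stated direction with a 20-point limit, the normal formula gives 31 to 50% and the exact score test 26 to 45%, across the two levels and 21 to 26 evaluable per arm. With a 10-point limit, the formula gives less than 20% throughout. Even with the favourable distance of 0.25, a two-sided 95% interval needs more than 26 per arm before any loss.

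These figures rest on the plan's assumed rates of 10% and 15% and, for 21 per arm, on its assumed 20% loss. That the sponsor used one-sided 5% is the closest arithmetical match, not an established fact.

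**What to change.** Before outcome data are analysed:

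1. State one level and its sidedness in the Sample calculation section and use the same level in a written decision rule under Methodology. For example: non-inferiority is concluded if the upper limit of the two-sided 95% confidence interval for the difference in complication rate, no-touch minus conventional, lies below the stated margin (one-sided alpha 2.5%). If a one-sided 95% bound was intended, say so and give one-sided alpha 5%. State the margin in percentage points and name the interval method.
2. Replace the 80% power claim with the power that 52 patients give at that level, before and after the assumed loss, with the expected difference in the stated adverse direction.
3. Do not record that 52 was calculated at one-sided 5% unless the sponsor confirms it from the calculator settings. If the settings are available, report them.

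The cost is a few sentences; restating the power adds no patients. The downside is that the stated power becomes much less favourable. Keeping 80% power in the stated direction with a 20-point limit would instead take 144 to 150 patients at one-sided 5%, or 184 to 190 at one-sided 2.5%, with loss included.
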